6.4. Subjects Identification and Randomization

6.4.1. Screening No.

The unique subject identification (SID) number will be assigned to all screened subjects. The SID number consists of 4 digits and is numbered sequentially from X001 (X is institution's number.). The SID number is given in the order of subject screening (according to order consent of participation when the screening conducts in the same day.). The SID number would be managed from screening to randomization. The subject who has been withdrawn from this study prior to randomization and after screening will retain their SID number.

6.4.2. Randomization No.

The subjects enrolled in this study would be assigned randomly to each treatment group. The randomization code will be generated by biostatistics staff who are not related to this study, (independent to this study), using statistic software (SAS®, latest version) and block randomization method considering the predefined block size. Subjects in Part 1 will be assigned to HM15136 and placebo in a 3:1 ratio, in the case of Part 2, up to 66 subjects will be assigned to HM15136 and placebo. Thirty (30) subjects in Cohort 4 will be assigned in a ratio of 1:1 and 12 subjects in each Cohort 5-7 will be in a 3:1 ratio according to rules below in Table 1.

After the signing of informed consent, the investigator assigns the randomization number in the order of subjects who meet the in/exclusion criteria and are selected for participation. According to the protocol, the randomization number is given on Day -1 or Day -2, prior to administration of IP. The randomization number is kept in a limited place accessible only by pharmacy staff and can only be accessed by other personnel if the blind is broken. The randomization number includes the 3 digits of subject's number as presented in the below table.

Table 1. Randomization No. and Treatment Assignment

Part	Cohort	Randomization No.	Treatment Assignment*	
Part 1	1	101 - 112	HM15136 0.02 mg/kg (N=9)	Placebo (N=3)
	2	201 - 212	HM15136 0.04 mg/kg (N=9)	Placebo (N=3)
	3	301 - 312	HM15136 ≤0.08 mg/kg (N=9)	Placebo (N=3)
Part 2	4	401 - 430	HM15136 0.06 mg/kg (N=15)	Placebo (N=15)
	5	501 - 512	HM15136 ≤0.02 mg/kg (N=9)	Placebo (N=3)
	6	601 - 612	HM15136 ≤0.04 mg/kg (N=9)	Placebo (N=3)
	7	701 - 712	HM15136 ≤0.06 mg/kg (N=9)	Placebo (N=3)

* In Part 1, dosage of Cohort 3 can be adjusted, but not be over the dosage presented in the table. The escalated dose should not be over twice the dose of the previous cohort.

* In part 2, if necessary, after the review of the safety data obtained by the 9th subject's visit on Day29 of Cohort 3 in Part 1, the cohort can be processed within the 0.06mg/kg dose.

The dose and study progress of Part 2 should be guided by the recommendations of the DMC. After the review of the safety data in Part 1, Part 2 may not proceed.

Once a randomization number has been assigned to one subject, the number cannot be assigned to another subject. If subject participation is withdrawn early and the subject is replaced under the direction of the sponsor, an alternate randomization number is assigned when the replacement subject successfully completes the screening. The randomization number of the replaced subject is generated so that it can be assigned to the same treatment group as the discontinued subject. The randomization number is divided into a total 3 digits with a 'Cohort No. (1 digit) + Enrollment order (2 digits).' Iterated randomization numbers are made up of a total 4 digits, with '1' added to the beginning of the randomization number of the subject whose participation is to be withdrawn. For example, if replaced the subject 202, the randomization number of the alternative subject would be 1202.

6.5. Blinding and Unblinding

Although this study is conducted in a double blind, those who are responsible for preparation of IP are excluded. These staff are not involved in any other activity in this study.

On a subject level, during the conduct of the study, unblinding may be conducted only for the subject who have medical emergencies that can be a problem for the subject's safety (in the case of knowing the information of IP administered to the subject may affect the treatment of the emergency situation), or DLT (Dose limiting toxicity) occurred, or for determining whether to increase or decrease dosage as specified in the protocol and/or needed for the assessment of the DMC. Except for these reasons, unblinding should not occur on a subject level. The investigator must contact the principal investigator and Hanmi Pharm. Co., Ltd. to discuss this issue before the unblinding takes place. Emergency unblinding can be performed by the principal investigator using the IWRS. It should be ensured that no study personnel is unblinded to other subjects. Study site personnel and Sponsor personnel directly associated with the conduct of the study will not be unblinded. The investigator should record the date and reason why unblinding occurred in the CRF

If the investigator, or the staff performing evaluations, or a subject that is not kept in blind, this subject should be withdrawn from this study. And if unblinding occurred prior to completion of this study accidentally or caused by SAE, the investigator should record this issue and provide prompt notice to Hanmi Pharm. Co., Ltd. However, if it is judged that the ethical reason or the unblinding effect on the safety of the subject is small, the subject can continue to participate in the study in judgement of investigator with Hanmi Pharm. Co., Ltd.

Due to COVID-19 outbreak, an interim analysis based on partially validated data for Part 1 will be performed for administrative purpose prior to database lock of Part 1. For this planned interim analysis, unblinding will occur after partially validated data transfer for Part 1.

Designated personnel not involved in the study conduct will perform the interim analysis. Only authorized members who are listed in the Interim Analysis Unblinding and Information Dissemination Plan will have access to review the summary tables or figures of the interim analysis results, in which the information is presented in a grouped fashion with the actual treatment, e.g., mean treatment effect.

Unblinding for final analysis of each part will also occur after the corresponding database locks for each Part 1 and Part 2. The final analysis for each part will be performed separately, once each part is completed.

For details please see section 11.3.1. Interim Analysis.

7. Completion and Early Discontinuation of the Clinical Trial

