5.4.2. Subject's Withdrawal, Replacement and Discontinuation

The subject may withdraw his/her consent to participate in the clinical trial at any time for any reason without any disadvantage or impact on future medical care. Although the subject is not required to state the reasons for withdrawing consent to participate in the clinical trial, the reasons for withdrawal must be recorded in all cases. If the randomization code for the subject is broken, the date, time and reason must be recorded. Subject's participation may be terminated before completion of the study.

Subjects who have received IP but for whatever reason cannot participate in the entire study period are classified as 'withdrawals'.

If the subject requests the study discontinuation or consent withdrawal or the investigator judges that the subject should be discontinued, the subject may be withdrawn at any time. If the study would be discontinued or withdrawn, the results of the study obtained prior to that point in time may be reviewed for final evaluation if assessable.

The reasons for the withdrawals or discontinuation of individual subjects are as follows.

- 1) If the subject who is healthy in Part 1 has a FPG exceeding 10 mmol/L (180 mg/dL). Subjects FPG should be re-tested and FPG must be confirmed by a morning plasma glucose level (after 10 hours of fasting) that is \geq 180 mg/dL (10.0 mmol/L), verified by a standard laboratory analysis (ie, YSI glucose analyzer at the site). Subjects who have confirmed FPG values that have reached the threshold limits will be counseled first. They will then have their FPG re-assessed, per PI discretion. If the FPG is still above the threshold they will be dropped from the study and may be replaced.
- 2) If the subject who has type 2 DM in Part 2 has an FPG exceeding 15 mmol/L (270 mg/dL). Subjects FPG should be re-tested and confirmed by a morning fasting plasma glucose level (after 10 hours of fasting) that is \geq 270 mg/dL (15.0 mmol/L), verified by a standard laboratory analysis (ie, YSI glucose analyzer at the site). Subjects who have confirmed FPG values that have reached the threshold limits will be counseled first. They will then have their FPG re-assessed, per PI discretion. If the FPG is still above the threshold they will be dropped from the study and may be replaced.
- 3) Difficult to keep taking part in the clinical trial due to any adverse events (AE).
- 4) Violation of protocol
- 5) Impossible to follow up on a subject.

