- 6) Withdrawal of consent by subject or legally acceptable representative.
- 7) In case of discontinuation by the sponsor
- 8) If the investigator judged that it is difficult to continue this study.
- 9) If the subject is pregnant.
- 10) Participation of subject who is not acceptable per inclusion and exclusion criteria.
- 11) Administration of prohibited medications, or necessary to administer it.
- 12) Treatment of prohibited therapies, or necessary to treat with them.
- 13) Poor medication compliance.
- 14) Others
- 15) If missing dosing and/or visits occurs for many times (due to COVID-19 or any other inevitable reasons), The study investigator may withdraw or discontinue a subject from participation in the study, if the subject missed a specific numbers of dosing/dosing visits. Missed doses $<70\%$ may lead to discontinuation of subject, based on decision of investigator and sponsor. If a subject must miss dosing due to COVID-19 or any other unavoidable reasons, the willingness and safety of the subject will be taken into consideration.

If for any reason during the study period the subject is withdrawn from participation or dropped the study prior to completion, the investigator should make every effort to conduct the planned evaluation in the follow-up visit. If possible, early termination visit is planned within 1 - 3 days after discontinuation of IP. Last IP administration date, withdrawal reason and all of information until the termination point should be recorded in source documents (SD) and Case Report Form. In order to prevent omissions of any adverse events, the investigator should contact the withdrawn subject via phone calls, letters (or e-mail), direct visits, etc., and leave relevant records. Also, even if tracking is not possible, try to contact as much as possible to minimize follow up failure and leave relevant record. In case of withdrawal caused by AE, should be followed until recovered (or the investigator judges normalization) or until the subject's last visit completion, or until further follow up is judged to be meaningless. Particularly, in case of withdrawal caused by elevation of FPG corresponding to the reason 1) and 2), IP should be stopped and follow up occur until FPG recovered or judged to be normal with the subject's consent. If the investigator made the subject withdraw participation, that subjects cannot re-participate in this study.

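### Withdrawal from the study is the default after unblinding, so subjects unblinded for an emergency or DLT lose their remaining scheduled safety, PK and antibody visits

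*Protocol*

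**What the plan says.** Protocol 6.5 first limits subject-level code breaks. During the study "unblinding may be conducted only for the subject who have medical emergencies that can be a problem for the subject's safety", "or DLT (Dose limiting toxicity) occurred, or for determining whether to increase or decrease dosage as specified in the protocol". A need of the DMC is a further ground. Emergency code breaks are made by the principal investigator in the IWRS.

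The section then sets the consequence: "If the investigator, or the staff performing evaluations, or a subject that is not kept in blind, this subject should be withdrawn from this study". The next sentence adds that "if unblinding occurred prior to completion of this study accidentally or caused by SAE, the investigator should record this issue" and tell the sponsor. The paragraph closes with an exception. Where the ethical reason, or the effect of unblinding on the subject's safety, is judged to be small, "the subject can continue to participate in the study in judgement of investigator with Hanmi Pharm. Co., Ltd". SAP 2.2 repeats both the default and the exception.

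Protocol 5.4.2 handles the same event differently: "If the randomization code for the subject is broken, the date, time and reason must be recorded". Its list of withdrawal reasons does not name a code break, though the list is open. For subjects who leave early, it says that "the investigator should make every effort to conduct the planned evaluation in the follow-up visit" and "If possible, early termination visit is planned within 1 - 3 days after discontinuation of IP". Protocol 10.1.1, item 7, makes the end-of-treatment (EOT) visit permissive. The Day 113 procedures may be done there, and items from other follow-up visits may be added on request.

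**The concern.** The rule links leaving the study to having had an event serious enough to break the code. Safety and tolerability are a primary objective, and the subjects caught by the rule are the ones most informative for it. If the drug causes the events, more of them will be on active treatment, so the missing later data would not be balanced between drug and placebo.

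Loss of blind is a poor reason to stop collecting these data. It can affect judgements such as causality or the grading of an injection site. It does not invalidate a laboratory value, a drug concentration or an antibody result.

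**Working it through.** The documents give no figure for this rule, so there is none to reproduce. The check compares the provisions and then gives a sense of scale.

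**1. Who is caught.** The withdrawal sentence applies when the investigator, the evaluating staff or the subject is no longer blind. The DMC is a separate unblinded body (Protocol 7.3), so its access does not by itself trigger the sentence. That leaves site-level code breaks, for which the permitted grounds are mainly emergencies and DLTs. Because the principal investigator performs the emergency code break, such a break leaves an investigator unblind for that subject, and the default applies.

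**2. What ends.** The sentence refers to withdrawal from the study, not only from study drug. Nothing in 5.4.2, 6.5, 10.1.1 or SAP 2.2 keeps a withdrawn subject on the remaining scheduled visits.

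**3. What remains.**
- Protocol 5.4.2: follow-up of an adverse event that caused the withdrawal, contact to pick up adverse events, a best-effort follow-up evaluation, and an early termination visit if possible.
- Protocol 10.4.8: adverse events are followed to resolution or stabilization, whatever their causality.
- Protocol 10.1.1, item 7: an optional EOT visit with Day 113 procedures. Under 10.2.1 these include PK, ECG, laboratory tests and immunogenicity.

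**4. Do 5.4.2 and 6.5 conflict?** Section 5.4.2 requires the code break to be documented and says nothing on whether the subject stays. Section 6.5 says the subject should leave. Both can be followed at once, so the sections are unreconciled but not contradictory. Separately, 5.4.2 demands a strong effort at the follow-up evaluation, while 10.1.1 only permits the EOT visit.

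**5. Scale.** The day of unblinding is an assumption.
- Share of a dose group: 1/9 = 11.1% in a cohort with 9 active subjects; 1/15 = 6.7% in Cohort 4 as planned.
- Antibody samples (Protocol 10.2.1): Days 1, 15, 29, 57, 78, 85 and 113, so 7 in all. Still to come after Day 8: 6 of 7. After Day 29: 4 of 7 (Days 57, 78, 85, 113). After Day 57: 3 of 7. One EOT visit could recover about one.
- PK samples (COVID-19 schedule, 25 in all): 13 remain after Day 29. Six of these are timed from the 12th dose (Day 78 post-dose, Days 80, 82, 85, 99 and 113), and the other 13 − 6 = 7 are pre-dose samples. If study drug has stopped, the six would not exist as planned whatever the blinding rule says, and the same holds for the post-dose ABPM and Holter period of Days 78 to 82. The antibody count is therefore the cleaner measure.

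**The case against.** The case against has four parts.

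- **Follow-up does not stop.** A reader might infer from 6.5 that an unblinded subject loses all further safety, PK and antibody assessment. The documents do not support that. Adverse event follow-up continues, a follow-up evaluation is to be attempted, and an EOT visit may include PK and antibody sampling. This stands, and it limits the loss to the remaining scheduled visits.
- **There is an exception.** It follows directly on the sentence about accidental or SAE-related unblinding, so discretion is available for serious events. This stands too, but continuation is not the default. The stated condition is unclear, and if it means that the effect on safety must be small, the most serious cases are the least likely to meet it.
- **5.4.2 has an open list.** A reader might see a contradiction with 6.5. There is none: the list ends with a catch-all, and recording a code break is compatible with withdrawing the subject.
- **The harm is not measured.** Counting every day from a code break to Day 113 as lost would ignore the follow-up above. It would also ignore that some subjects would leave because of the adverse event itself, and that samples tied to the 12th dose disappear if dosing stops. A reader might also expect such exits to be coded as unblinding and not as the adverse event. The documents give no CRF reason list, so that is conjecture.

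In addition, every dosed subject stays in the safety population and the safety analysis is descriptive with individual listings, so an affected subject remains visible up to withdrawal. That reduces the effect on the analysis but does not supply the missing later data.

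**Conclusion.** The point holds in a limited form. Followed as written, 6.5 and SAP 2.2 by default take the remaining scheduled safety, PK and antibody visits away from subjects unblinded at the site, and the permitted grounds make these mainly subjects with emergencies or DLTs. Adverse event follow-up, one best-effort evaluation and an optional EOT visit remain.

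The size cannot be derived, because the documents give neither the frequency nor the timing of unblinding, nor how often the exception would be used. The 11% share and the antibody count show what one such subject could mean in a 9-subject group; they do not estimate the expected loss. The conclusion rests on reading the default literally. It is a worthwhile low-cost clarification and does not invalidate the design.

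**What to change.** In Protocol 6.5 and SAP 2.2, separate loss of blind from leaving the study:

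- State that unblinding alone does not end participation in the remaining scheduled safety, PK and immunogenicity assessments to Day 113, consent permitting.
- Record who was unblinded and when, in addition to the reason.
- Flag later judgement-based assessments, such as causality and injection site grading, in the listings.
- Reconcile 6.5 with 5.4.2 on what a code break triggers, and reword the condition for continuation so that it can be applied.
- Reconcile the strong wording on the follow-up evaluation in 5.4.2 with the permissive wording on the EOT visit in 10.1.1.

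Whether study drug continues after unblinding stays under the protocol's own clinical rules and is not part of this change.

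The cost is new wording in 6.5 and SAP 2.2, the two reconciliations and a listing flag. The downside is that some assessments after unblinding are not blind, which the flag makes visible.

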7.1. Study Completion

The end of entire study termination defines as the last subject's study completion or the withdrawal of consent, follow-up failure, or termination caused by death. If it is judged that each subject completed the procedure of administration/visit schedule totally 22 weeks included treatment period for 12 weeks and the follow-up period, and evaluation of clinical laboratory test at the last visit, and resolve the AE occurred or proceeding at the last visit, or no further follow up is meaningful, that subject is considered to complete the study.

7.2. Study Discontinuation

If the investigator or sponsor or medical monitor got to know any situation or events that there is a potential risk to the subject if the study was continued, they may be terminated the study after appropriate discussion. Even if the above conditions are not met, the study may be terminated according to the sponsor's judgement. If the subject's safety is threatened, the study must be stopped/terminated. The sponsor has the right to terminate this study at any time for failure to enroll a targeted number of subjects or for safety or other administrative reasons.

7.3. Dose Escalation and Study Stopping Criteria

<Dose Escalation Stopping Criteria>

The procedure for determining the dose is as follows

- The main criterion for determining tolerability is emesis/vomiting (=gastrointestinal tolerability).
- Vomiting is associated with the pharmacologic administration of GLP-1 agonists and glucagon, and the severity of vomiting in this study is defined as.:
 - Moderate: 3-5 times vomiting within 24 hours (when the vomiting interval is at a minimum of 5 minutes or more, each vomiting event is counted.)
 - Severe: 6 times or more within 24 hours or requiring fluid injection via IV (intravenous) (when the vomiting interval is at a minimum of 5 minutes or more, each vomiting event is counted.)

If one of the following criteria is met, an independent DMC will meet to assess safety in real-time and make dosing and cohort escalation assessments and recommendations, such as: IP administration and dose elevation should be stopped, or the dose level should be discontinued, suspended, or a dose modification or repetition should occur prior to proceeding to subsequent dosing, or dosing can continue. All decisions to increase the dose or discontinue dosing will be decided by the DMC. The DMC will determine when the safety and/or tolerance limits have been reached.

- 1) Moderate or severe emesis occurred in 50% or more subjects in one cohort.
- 2) Severe emesis occurred in 25% or more subjects in one cohort.
- 3) At any time, if one subject dies (CTCAE grade 5 toxicity may be used as a grading scale) in one cohort.
- 4) If severe AEs (CTCAE grade ≥ 3 may be used as a grading scale) occurred in 2 subjects within one cohort.
- 5) If moderate AEs (CTCAE grade ≥ 2 may be used as a grading scale) occurred in 2 subjects within one cohort and persisted for 7 days or more.
- 6) If a SAE occurred in 1 subject or more within one cohort.
- 7) If clinically significant similar laboratory abnormalities, clinically significant ECG or V/S abnormalities, or severe AEs in the same SOC (System organ class) occurred in 2 subjects or more receiving IP representing dose limiting toxicity (DLT).

As the DMC is unblinded, any potential stopping rule event occurring in subjects receiving placebo would not be considered to be meet the stopping rule. Additionally, AEs considered to be unrelated to HM15136 would not be considered to meet the stopping rules.

< Data Monitoring Committee (DMC) >

The DMC is a specific committee for the study and will function for safety review and dose escalation decisions as described above. The operations of the DMC will be defined in the DMC charter.

The DMC will review safety data (adverse events, clinical laboratory, vital signs and electrocardiograms, and other unblinded relevant data). There will be 3 dose decisions. In addition the DMC will have unplanned meetings should stopping criteria appear to have been met.

After Cohort 1 randomization is completed, the DMC will assess the safety and will make dosing and cohort escalation assessments and recommendations to decide whether subjects can be randomized into Cohort 2.

Dose escalation from cohort 2 to next dose level for the subsequent Cohort 3 will be based on the safety, tolerability, available PD, and available PK data obtained from cohort 1 and through the 9th subject's visit on Day 29 in cohort 2. The DMC will make recommendations for the decision whether subjects can be randomized into Cohorts 3.

The next dose level for the subsequent cohort (Cohorts 4 in Part 2) will be based on the safety, tolerability, available PD, and available PK data obtained from cohort 1, 2 and through the 9th subject's visit on Day 29 in cohort 3. An independent Data Monitoring Committee (DMC) will assess the safety and will make dosing and cohort escalation assessments and recommendations.

< Data Review Meeting >

A data review meeting will be held by sponsor, investigator and medical monitor to review safety data after the 9th subject of cohort 5 and 6 in Part 2 has completed their Day 43 visit. This time point is situated 6 weeks after the first dosing. safety data review will guide the decision for dosing and cohort escalation recommendations.. Additionally, a second DRM will be held and safety data from the 12th subject's final visit on Day 113 (=F/U Visit) will be reviewed to dose escalate.

Dose escalation from cohort 6 to the subsequent cohort 7 will follow the same dose escalation scheme and DRM(s) of the previous cohort.

Cohorts 6 and Cohort 7 may be conducted at doses of 0.04 mg/kg and at 0.06 mg/kg respectively upon approval by the Investigator, Medical Monitor, and the Sponsor, if the safety is demonstrated in Cohort 5.

If sufficient safety data are collected after cohort 5 or cohort 6 have been completed, no additional cohorts will be conducted, and sponsor may choose to complete study.

< Study Stopping Criteria >

In addition to the DMC, during the study the investigator and the sponsor may suspend the study after appropriate discussion, due to but not limited to, the following situations or events, and submit to the IRB a sufficient written statement of reasons for the termination of the study.

- 1) When any obvious or unacceptable risks to the subjects enrolled in this trial are found.
- 2) If the sponsor decides to suspend or hold the development of IP.

8. Information and Control of Investigational Product

